The team will compare the monitoring parameters listed above to identify demographic data, epidemiological data, and correlations with the use of naloxone rescue kits. Differences between ASAP in categorical variables (utilization of naloxone auto-injector, utilization of EMX-run and emergency room visit during study period, gender, race, ethnicity, education level, marital status, results of physical examination [normal vs. abnormal], presence of substance abuse) will be tested by Chi Square test or Fisher exact test where appropriate. Differences in continuous variables (e.g., age, RIOSORD scores) will be tested by independent two samples, Student's *t* test, or Wilcoxon Rank Sum test, where appropriate. *P* values of less than 0.05 were considered statistically significant.

14. Provisions to Monitor the Data to Ensure the Safety of Subjects

In accordance with the IRB at UNM HSC, the investigators commit that the data will be used only for the research purpose. The data will be disclosed to all study investigators. The investigators will use PowerChart to obtain necessary information, such as past medical history, family history, and concomitant medications. The investigator will keep a patient log ("log book", Appendix 7) to track patients' consequent clinic visits. The investigators will use paper- and electronic-based data collection during their face-to-face interviews. All data will be transferred to REDCap system. The paper-based data and the log book will be stored in a locked cabinet in physician's office ([name]) at UNM ASAP. The paper- and electronic-based database and Excel file will be destroyed upon completion of data analysis. The study medication is stored in another locked cabinet of the same office. This room is also locked and only a few employees (charge nurse, study coordinator, PI, medical director) have access to open the room each day. Reported adverse reactions from naloxone for opioid overdose were tremor and hyperventilation associated with an abrupt return to consciousness.¹⁶ We will ask if study subjects experience withdrawal symptoms at their clinic visits. The frequency of these adverse reactions is unknown. These adverse reactions are not life-threatening, and hyperventilation will be managed with rescue breathing. This topic is included in patients' education in this study.

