[name], [name] and [name] will be responsible for data storage and will share the data with other IRB-approved investigators on an as needed basis. [name] and [name] may share the data with a biostatistician at the Clinical Translational Science Center for the purpose of data analysis. The biostatistician will follow HIPAA regulations and keep the data in accordance with the data storage policy at CTSC.

17.Data and Specimen Banking

In accordance with the IRB at the UNM Health Science Center (UNM HSC), the investigators commit that the data will be used only for the research purpose and not to identify individual study subjects. The investigators will use minimum identifiers (e.g., date of birth, last clinic visit) to protect the identity of the participants.

18. Risks to Subjects

The research team assumes the following risks during the study: adverse reactions from naloxone and loss of confidentiality.

1. Adverse reactions from naloxone

Reported adverse reactions from naloxone for opioid overdose were tremor and hyperventilation associated with an abrupt return to consciousness.¹⁶ According to the package insert, the abrupt reversal was described as follows: "Abrupt reversal of opioid effects in persons who were physically dependent on opioids has precipitated signs and symptoms of opioid withdrawal including: body aches, fever, sweating, runny nose, sneezing, piloerection, yawning, weakness, shivering or trembling, nervousness, restlessness or irritability, diarrhea, nausea or vomiting, abdominal cramps, increased blood pressure, tachycardia." The frequency of these adverse reactions is unknown. These adverse reactions are not life-threatening, and hyperventilation will be managed

18 [Type text]

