with rescue breathing. This topic is included in patients' education in this study. The research coordinator and clinician will discuss the signs and symptoms of a near fatal overdose (slowed breathing, pallor, lack of responsiveness, inability to follow directions, etc). We provide validated materials to the patients from kaléo (Appendix 2) and Substance Abuse and Mental Health Services Administration (Appendix 9) related to opioid overdose which they can take home and study as well. A "practice" naloxone autoinjector is then used in the clinic so that the patient and his/her bystander can understand how it might be used in an emergency and life threatening situation. In the event of emergency Naloxone use, the autoinjector speaks to the patient through the procedure so it can help with the delivery of the medication. Distribution of the naloxone rescue kits and providing appropriate education on drug overdoses will potentially save lives of patients in New Mexico who took onioids

overdoses will potentially save lives of patients in New Mexico who took opioids. Naloxone auto-injector enables patients and their bystanders to provide naloxone immediately without the utilization of healthcare institution for the administration of intravenous naloxone. Additionally, the intramuscular administration route is an easy and effective way to deliver medication with minimum drug degradation.

2. Loss of confidentiality

The research team will make efforts to protect patient-related information as much as possible. The research team collects patient information, such as demographic information, use of opioids, and use of illegal drugs. The research team will not use a patient's name or any information that might reveal the identity of the patient. The research team will create a specific ID (i.e., first letter of study site, enrollment number (3-digit); e.g., A001) for each patient to minimize using a patient's name. Additionally, as stated in Section 26, all paper-based study data will be kept in a locked cabinet at UNM ASAP. Electronic data will be kept in a secured computer system in [name] office (UNM College of Pharmacy, Room B21B) and [name] office (Clinical Neuroscience Center).

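### Sections 14 and 18 give rescue breathing as the management of hyperventilation on waking after naloxone, a measure the protocol otherwise links only to overdose

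*Combined protocol and SAP*

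**What the plan says.** Section 14 (Provisions to Monitor the Data to Ensure the Safety of Subjects) and Section 18 (Risks to Subjects, item 1) give the same account. The reported reactions to naloxone given for overdose are "tremor and hyperventilation associated with an abrupt return to consciousness". On frequency, both say: "The frequency of these adverse reactions is unknown". On management, Section 14 says: "These adverse reactions are not life-threatening, and hyperventilation will be managed with rescue breathing". Section 18 has the same sentence, split by a page break: "These adverse reactions are not life-threatening, and hyperventilation will be managed", then "with rescue breathing. This topic is included in patients' education in this study". Section 14 also places the topic in patient education.

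Further on, Section 18 lists the signs of a near fatal overdose that staff discuss with subjects: "slowed breathing, pallor, lack of responsiveness, inability to follow directions". On teaching materials it says: "We provide validated materials to the patients", naming the manufacturer (Appendix 2) and a federal agency (Appendix 9) as the sources. It adds that a practice auto-injector is used in the clinic and that the device gives spoken guidance. Section 14 has one follow-up provision on reactions: "We will ask if study subjects experience withdrawal symptoms at their clinic visits".

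**The concern.** Rescue breathing supports someone who is not breathing adequately. Sections 14 and 18 assign it to someone who has just regained consciousness and is breathing too fast. It is also the only management that the available text gives for this named reaction, so the stated safety rule ought to be right.

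The setting makes the wording worth checking. Reversals happen away from the clinic: the Year 1 account in Section 2 reports 82, of which 81 were in community members and one in a study patient. Whatever is done when a person wakes will usually be done by a lay responder. The Study Procedures text offers education to bystanders as well, and subjects who enrol without one are asked to pass the teaching on to family and friends. If the teaching script carried the error, it could spread with no clinician present to correct it.

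**Working it through.** No figure in the plan depends on this point, so the check is textual: find each use of the term rescue breathing in the available text and note the condition it is said to manage.

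| Place | Condition it is tied to |
|---|---|
| Section 2, account of the Massachusetts programme | Overdose: content of that programme's overdose training |
| Section 14 | Hyperventilation on waking after naloxone |
| Section 18, item 1 | Hyperventilation on waking after naloxone |
| Section 19 | Overdose: managing its symptoms |

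Count: 2 (hyperventilation) + 2 (overdose) = 4.

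Next, compare the two states the protocol describes.

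- *Overdose.* Section 18 gives slowed breathing and lack of responsiveness. Section 2 refers to respiratory depression.
- *The reaction in question.* The person has woken suddenly and is over-breathing.

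These are opposite in both breathing and consciousness. One measure is named for both.

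Then consider the likely slip, that *hypoventilation* was meant. Rescue breathing would then fit. But the reaction named just before is hyperventilation on waking, and the sentence calls the reactions not life-threatening, which sits badly with under-breathing after an opioid overdose. On this reading the condition is misnamed in both sections; on the other the management is wrong. Either way the sentence must change.

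Last, look for a correction elsewhere. Section 19 ties rescue breathing to overdose, so it conflicts with Sections 14 and 18 and does not repair them. The question about withdrawal symptoms at clinic visits looks back on events. The adverse-reaction assessment in Section 24 (Naranjo, CTCAE v4.0) judges causality and severity. Neither tells a responder what to do. No available text corrects the sentence.

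**The case against.** The strongest reply is that this is one loosely drafted sentence, probably copied from one section to the other, and that it tells us nothing about what subjects learn. Study Procedures lists the teaching content as recognising overdose, its risks, and use of the auto-injector; management of hyperventilation is not on the list. The handouts come from the manufacturer and a federal agency and are described as validated. The phrase about the topic being in patient education could refer to adverse reactions in general or to rescue breathing itself. Oversight also exists beyond this sentence: reactions are to be reported at visits and assessed, and a safety board meets every three months and at once for an unexpected reaction.

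The count can be criticised too. It shows inconsistent use of a term; that the management is wrong also needs basic clinical knowledge. One of the two overdose uses describes another programme's training, and the Section 19 sentence is itself awkward.

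Much of this stands. It limits the point to the wording of a safety rule and leaves its cause and reach unproved. It does not rescue the sentence, which is wrong on either reading. The oversight provisions do not manage the reaction, and two sections do say that the topic is taught, so one check of the script is reasonable.

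**Conclusion.** The point holds and is minor. Confidence is high that the mismatch exists; its cause (wrong management or wrong word) and its consequence are not established. The extent is one sentence in two sections, 2 of the 4 uses of the term in the available text. No number of affected events can be given because the protocol states the frequency as unknown, and the documents do not say how many subjects and bystanders were taught. Endpoints, power and analyses are untouched.

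Two limits apply. Part of the text between Sections 9 and 12 was not available, so the count and the absence of a correction are confirmed only for the rest. Appendices 2 and 9 were not available either, so the actual teaching could not be compared with the sentence.

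**What to change.** In Sections 14 and 18, delete rescue breathing as the management of hyperventilation. State that rescue breathing is for an unresponsive person whose breathing is slowed or absent. Ask a study clinician to write the instruction for a person who has woken and is breathing fast. Check once that the education script agrees with Appendices 2 and 9, and correct the teaching, including that given to bystanders, only if the script carries the error.

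The cost is an edit to two sentences, a short piece of clinical wording, one check of the script and a routine IRB amendment. If the script is sound, nothing more is needed. If it is not, the cost of re-teaching cannot be estimated from the documents.

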that New Mexico ranks third in the United States for the rate of accidental overdose deaths associated with prescribed opioid use, this attention is warranted. Prescribing intramuscular and intranasal naloxone rescue kits to high risk patients receiving chronic opioids to treat chronic pain has been employed recently as one effort that might decrease the accidental overdose rate associated with these medications. In past studies, risk stratification criteria have been employed to select patients on chronic opioid therapy who may benefit most from the use of an intramuscular or intranasal naloxone rescue kit. This method could inadvertently exclude patients who also may benefit from this therapy. Patients who do not fit the current definition of high risk criteria, such as anyone on chronic opioid therapy with comorbid dementia who forgets they already have taken their opioid mediation and the takes a second dose, or a patient whose metabolism of an opioid is changing, still may be at risk for adverse events associated with chronic opioid therapy. Rather than using inclusion criteria to select patients who receive naloxone auto-injector, a model that does not define "high risk" patients a priori, may offer improved benefits from the use of naloxone auto-injector. If a "universal precautions" method is employed, much in the same manner as epinephrine injection dispensed to patients with a history of anaphylaxis, or a glucagon pen and/or glucose tablets being dispensed to patients who use insulin to treat diabetes, the prescribing of naloxone auto-injector to all patients on chronic opioid therapy for chronic pain may have a greater impact on the accidental overdose morbidity/mortality rate associated with the use of chronic opioid therapy. Additionally, it may be beneficial to make naloxone available as a universal precaution for people who were not prescribed opioid to decrease mortality due to drug overdose. According to previous naloxone studies, a significant amount of opioid mortality occurs among those for who the opioid wasn't prescribed.^{11,12}

Year 1- ASAP Study

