Since April 2016, we have enrolled 358 patients at ASAP in our prospective nonrandomized clinical trial using the Evzio autoinjector. We have documented 82 overdose reversals thus far. Only one of the reported overdose reversals was from the study patients at ASAP, while the other 81 overdose reversals were from community members received naloxone from the study patients. For every 100 patients enrolled in the study, approximately 23 overdose reversals have been reported. We have submitted a peer-reviewed article about this data, and are now waiting to hear back regarding acceptance of the submission.

3. Study Design

- 3.1. The previous study at ASAP is a prospective observational study using the naloxone 0.4 mg auto-injector which took place April 4th, 2016 through April 30th, 2017.
- 3.2. Evaluation of patients enrolled include: # overdoses reversed, # naloxone doses needed, urine toxicology, history of overdoses witnessed, history of being reversed by naloxone, demographic information, medical history, etc.
- 3.3. For this current study, we propose the following new additional studies:
 - A biostatistical logistic regression analysis to study the characteristics of the study subjects who performed the overdose reversals (vs. the study subjects who did not).

8 | [Type text]

- A qualitative study to examine in-depth the characteristics of study subjects who a) documented many overdosed reversals/"saved" many community members, b) documented one overdose reversal/"saved" one community member, and c) did not document any overdose reversals
- Study the 2 mg Evzio autoinjector product to prospectively analyze the difference in doses (2 mg vs. 0.4 mg) needed to reverse an overdose. The goal will be to recruit 100 patients in one year and document between 20-30 overdose reversals in the community.

4. Inclusion and Exclusion Criteria

Inclusion Criteria

- A. All patients treated with naltrexone, methadone or buprenorphine as medication assisted treatment at the UNM Addiction and Substance Abuse Program (UNM ASAP) aged 18 or older.
 - Over 70% of patients at UNM ASAP on medication assisted treatment use methadone
- B. Subjects who sign a consent form.

Exclusion Criteria

- A. Subjects who are allergic to naloxone and its inactive ingredients.
 - Inactive ingredients: buffering agents
- B. Subject younger than 18.

5. Number of Subjects

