The team will handle sensitive information regarding illegal drug use of a patient and of his/her bystanders. The study team wants to emphasize that the information obtained for the study will not be reported to law enforcement authorities. The Certificate of Confidentiality, which insures patient's privacy, was issued by the National Institute of Health for UNM Pain Center and UNM ASAP.

19.Potential Benefits to Subjects

Because New Mexico has led the country in unintentional opioid overdose deaths and opioid misuse, finding appropriate prevention for drug overdose is critical. Distribution of the naloxone rescue kits and providing appropriate education on drug overdoses will potentially save lives of patients in New Mexico who now have an opioid substance use disorder. Intramuscular naloxone enables patients and their bystanders to provide naloxone immediately without the utilization of healthcare institution for the administration of intravenous naloxone. Additionally, the intramuscular administration route is an easy and effective way to deliver medication through the muscle with minimum drug degradation. Moreover, appropriate education will help study subjects identify symptoms of drug overdose and will manage associated symptoms, such as rescue breathing. In our patient education, we will emphasize that naloxone is to be used

for opioid overdose as an antidote for patients with chronic opioid therapy but not to be used as a means of rescue method for recreational opioid use.

By utilizing a "Universal Precautions" approach in this study, where any patient on chronic opioid therapy is given an intramuscular naloxone kit, the stigma attached to the use of intramuscular naloxone may be diminished. Additionally, this approach may have an impact on the prescribing of chronic opiate medication, to the point that any patient being prescribed chronic opiate medications will routinely be given a naloxone auto-injector --Much the same as any patient prescribed insulin receives glucose tablets and/or a glucagon pen. This would have the potential to dramatically increase the safety when opiate medications are misused.

20.Recruitment Methods

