We do recruit Native Americans but this research is not intended to target American Indian/Native populations nor is it conducted on tribal lands. While participants may be of these populations we are not seeking out these participants. We have a wealth of experience with persons of tribal descent and therefore we are sensitive to the local population in terms of tribal regulations, applicable laws and standards of professional conduct and practice.

32.Transnational Research

Not applicable

33.Drugs or Devices

Drug²³

- Generic name: Naloxone hydrochloride injection, USP
- Brand name: EVZIO

22 | [Type text]

- Strength: 0.4 mg/0.4 mL in each kit²¹ and 2 mg/0.4 mL in each kit²²
- NDC number
 - o 0.4 mg kit: 60842-030-01²¹
 - 2 mg kit: 60842-051-01²²
- Manufacturer: Kaleo
 - Richmond, VA 23219
- Pharmacology²⁴
 - Naloxone is an antidote of opioids and has been used frequently for patients whose condition is opioid intoxication or for patients with respiratory depression with therapeutic opioid doses. Several formulations are available: intravenous, intramuscular, and subcutaneous injections are commonly used administration routes. However, adverse events due to opioid overdose can occur at any time. Thus, a convenient drug formulation of naloxone is necessary to administer naloxone to prevent drug overdose deaths, regardless of a patient's knowledge.
- Pharmacokinetics
 - Time to peak: 15 minutes
 - Maximum serum concentration 1.24 ng/mL
 - Time to maximum concentration: 20 minutes
 - Metabolism:
 - Primarily metabolism route: liver via glucuronidation
 - Elimination half-life: 1.36 hours
 - Excretion: Urine (as metabolites)
- Indications²⁴
 - Emergency treatment of known or suspected opioid overdose, as manifested by respiratory and/or central nervous system depression.
 - Immediate administration as emergency therapy in settings where opioids may be present.
- Necessity of Investigational New Drug (IND) application
 - No. This product has an FDA approval in 2014.
- Drug storage
 - Naloxone auto-injector is stored at 15-25°C (59-77°F).²¹ Access to the naloxone auto-injector should be limited to the investigators at UNM ASAP.
 - The naloxone auto-injectors are stored in a secure area in the medication room in UNM ASAP. A pharmacist at UNM Investigational Pharmacy will maintain logs to track who the naloxone autoinjectors are dispensed for regulatory requirements (Appendix 7 and 8).¹⁷
- Drug destruction

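### Section 19 says patient education will stress that naloxone is not a rescue method for recreational opioid use; read literally, this contradicts the protocol's own indication of any known or suspected opioid overdose

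*Combined protocol and SAP*

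**What the plan says.** Section 19 (Potential Benefits to Subjects) states what the study's patient education will stress about naloxone in overdose, namely its use "as an antidote for patients with chronic opioid therapy but not to be used as a means of rescue method for recreational opioid use". This is current protocol text, and nothing in the supplied document withdraws it.

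Other sections describe the use of the product more broadly:

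- **Section 33 (Drugs or Devices, Indications)** gives two indications: "Emergency treatment of known or suspected opioid overdose", shown by respiratory or central nervous system depression, and "Immediate administration as emergency therapy in settings where opioids may be present". Neither depends on where the opioid came from or why it was taken.
- **Section 12 (Study Procedures)** describes the auto-injector as labeled for family members and caregivers to give as emergency therapy wherever there are opioids. It adds that under state law any bystander may give naloxone when an overdose occurs.
- **Section 16 (Monitoring Parameters, item 1c)** lists heroin, cocaine, methamphetamine and other substances among the circumstances of kit use to be recorded.
- **Section 2 (Innovation of Proposed Study)** suggests it may be beneficial to "make naloxone available as a universal precaution for people who were not prescribed opioid".
- **Section 19** itself goes on to claim the potential to "dramatically increase the safety when opiate medications are misused".

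**The concern.** The subjects are patients of an addiction program, enrolled because they are treated for opioid use disorder. The overdoses they are likely to meet, their own or other people's, may well follow non-medical use. An instruction that naloxone is not a rescue method for recreational use would, if believed, tell a lay responder to hold back in such a case. Section 2 says that the risk of death rises when treatment is not immediate, so even hesitation matters.

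The message can also travel. Under Section 12, subjects who enroll without a bystander are asked to teach their friends and family themselves. A misleading sentence in the clinic's education can then reach people whom the study team never meets.

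**Working it through.** No figure in the plan bears on this point, so the check compares texts. Take one case and ask what each section tells the person holding the auto-injector to do. The case: someone is found unresponsive and breathing slowly after taking heroin, or another person's tablets, for non-medical reasons.

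1. **Section 33, first indication.** This is a suspected opioid overdose with respiratory depression. Result: give naloxone.
2. **Section 33, second indication.** Opioids may be present. Result: give naloxone at once.
3. **Section 12, product description and bystander law.** Opioids are there and an overdose has occurred. Result: a family member or other bystander may give it.
4. **Section 16, item 1c.** If heroin was involved, that is a circumstance the study expects to record after the kit is used. Result: consistent with giving naloxone.
5. **Section 19, literal reading.** The opioid use was recreational, and naloxone is not to be a rescue method for that. Result: do not give it.
6. **Section 19, milder reading.** Nobody should plan recreational use on the strength of having naloxone to hand. Result: silent on what to do once an overdose has happened, so there is no conflict with steps 1 to 4.

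Steps 1 and 2 against step 5 are a direct contradiction about the same act. Step 3 points the same way as steps 1 and 2. Step 4 is an inconsistency of expectation: the data collection anticipates uses that the literal message would rule out.

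The other two statements are supporting context only. The Section 2 rationale concerns people without an opioid prescription, which is not the same as recreational users, and it says only that availability may help. The Section 19 remark about misuse describes a hoped-for effect on safety and gives no instruction on when to inject.

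Whether the contradiction reaches subjects depends on two conditions: that the sentence is taught as written, and that it is understood literally. The supplied text settles neither. Appendix 2 (the device guide) and Appendix 9 (the overdose toolkit) are not part of it. Their absence from the supplied text is not a fault of the plan, but it means that the actual teaching cannot be checked.

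**The case against.** The strongest reply is that the sentence is awkward prose with a sensible meaning: do not treat naloxone as a safety net that licenses recreational use. That reading is plausible, and it removes the conflict. The sections that describe the education also support it. Section 12 lists the content as signs and symptoms of overdose, its risks and how to use the device. Section 18 adds symptom recognition, practice with a training device and materials from the manufacturer and a federal agency. Neither contains an exclusion. The disputed sentence stands in a section on benefits, not in the procedures.

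This lowers the likelihood of harm but does not dispose of the point. The sentence says what the education will stress, and its words do not carry the milder meaning unaided. Sound handouts would not cancel a spoken message that contradicts them. If the milder meaning is intended, it can be stated plainly at no cost.

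A reader might be tempted to infer more, and three such inferences fail:

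- *That the wording excludes community members.* Section 2 reports that, apart from one reversal in a study patient, "the other 81 overdose reversals were from community members received naloxone from the study patients". But the sentence restricts by type of opioid use and does not mention community members, and Section 2 gives no reason for opioid use in any of these reversals. Nor is it stated whether the message was in use in Year 1. If it was, it did not prevent those 81, although a count of reversals cannot show rescues that were never attempted.
- *That the phrase about chronic opioid therapy shuts out the enrolled population*, defined in Section 4 as "All patients treated with naltrexone, methadone or buprenorphine as medication assisted treatment". The following paragraph of Section 19 describes this study's approach as one "where any patient on chronic opioid therapy is given an intramuscular naloxone kit", so the authors appear to use the phrase for their own subjects.
- *That reversals will be under-reported and the endpoints biased.* Nothing in the documents shows this. Routine questioning every three months, replacement of used kits and the Certificate of Confidentiality all work against it.

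**Conclusion.** The point holds as a conflict of wording with a conditional safety consequence. Read literally, the Section 19 message is narrower than the indication in Section 33 and the product description in Section 12, and it would be unsafe if followed. It should be corrected.

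The size cannot be given. The documents contain nothing from which to estimate how many overdoses, if any, would go untreated because of this sentence. The conclusion assumes only that an education message should be safe on its plain meaning for a lay audience. It does not assume that the sentence was taught, that anyone understood it literally or that harm occurred. The documents do not support a finding that subjects are in fact told to withhold naloxone, and none is made here. No endpoint, eligibility rule, sample size or analysis is affected.

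**What to change.** Replace the Section 19 sentence with wording such as: *use the auto-injector for any known or suspected opioid overdose, whatever the source of the opioid or the person affected; having naloxone does not make opioid use safe.* This keeps the caution that the authors probably intended and removes the apparent exclusion.

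Then check the education script, and any handout the team has written itself, against the new text. If the old message was taught, give the corrected one at the subject's next three-monthly visit, where Section 12 already provides for face-to-face education as needed. Ask subjects to pass the correction on to anyone they have taught.

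The cost is one sentence in the protocol, a check of the script and, where needed, a few minutes at a visit that is already scheduled.
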